8.1.2 Adverse Device Event (ADE)

Adverse event related to the use of an investigational medical device. This includes adverse events resulting from insufficient or inadequate instructions for use, deployment, implantation, installation, or operation, or any malfunction of the investigational medical device.

8.1.3 Device Deficiencies

Inadequacy of a medical device with respect to its identity, quality, durability, reliability, safety or performance.

8.1.4 Serious Adverse Events

An adverse event that:

- led to a death,
- led to a serious deterioration in the health of the participant that resulted in:
 - a life-threatening illness or injury,
 - a permanent impairment of a body structure or a body function,
 - hospitalization or prolongation of existing hospitalization,
 - medical or surgical intervention to prevent permanent impairment to body structure or function,
- led to fetal distress, fetal death, a congenital abnormality, or birth defect.

Note: Planned hospitalisation for a pre-existing condition, or a procedure required by the CIP, without serious deterioration in health, is not considered a SAE.

8.1.5 Serious Adverse Device Effect (SADE)

A serious adverse event (SAE) that is related to the device as described in Section 8.2 below.

8.1.6 Unanticipated Serious Adverse Device Effect (USADE)

Any serious adverse effect on health or safety, or any life-threatening problem or death caused by, or associated with a device, if that effect, problem, or death was not previously identified in nature, severity, or degree of incidence in the investigational plan. All reported

events will be followed until resolution, stabilization or 90 days after the last participant enrolled has completed the trial, whichever occurs first.

8.2 Adverse Event Relationship

For all collected AEs, the clinician who examines and evaluates the study participant will determine the AE's causality based on temporal relationship and his/her clinical judgment. Anticipated AEs are listed in Section 7.1. The investigator will use the definitions shown in the tables below to assess the relationship of the adverse event to the use of study device, and to assess the relationship of the adverse event to the study procedure. For purposes of this study, "device-related" or "procedure-related" will be defined as adverse events graded "probable" or "highly probable" in their relationship to the study device or procedure.

Table 3: Adverse Event Device Relationship

Relationship	Description
Not Related	
 Not associated with device application Due to an underlying or concurrent illness or effect of another device or drug
Unlikely	little or no temporal relationship to the study device and/or a more likely alternative aetiology exists
Possible	temporal sequence between device application and event is such that the relationship is not unlikely or patient's condition or concomitant therapy could have caused the AE
Probable	temporal sequence is relevant or event abates upon device application completion/removal or event cannot be reasonably explained by the patient's condition
Highly Probable	temporal sequence is relevant and event abates upon device application completion/removal or reappearance of the event on repeat device application (rechallenge the system)

Table 4: Adverse Event Study Procedure Relationship

Relationship	Description
Not Related	Not associated with procedure
Unlikely	little or no temporal relationship to the procedure
Possible	temporal sequence between procedure and event is such that the relationship is not unlikely or patient's condition or concomitant therapy could have caused the AE
Probable	temporal sequence is relevant or event abates upon procedure completion/removal or event cannot be reasonably explained by the patient's condition
Highly Probable	temporal sequence is relevant and event abates upon procedure completion/removal or reappearance of the event on repeat procedure.

8.3 Assessment and Documentation of Adverse Events

Qualified investigators and research staff will closely and carefully monitor study participants for all anticipated and any unanticipated adverse events. Any adverse event (whether or not related to the investigational device) or device deficiency should be recorded on the appropriate eCRF. All adverse events will be reported from the moment a consented participant has ELS Acoustic Enhancer material enter the body, through to participant study exit. Frequent follow-up visits during the first week following the ELS procedure (at days 1, 2, 3 & 7) and then at days 14, 30 and 90, will enable the investigators and research staff prudent monitoring of participant safety.

Investigational sites will be asked to report the final medical diagnosis as an AE, rather than reporting all signs and symptoms as separate events.

It is the responsibility of the investigator to decide when an adverse event has occurred. Adverse event information will be collected throughout the study. Adverse events will be recorded on the appropriate CRF by the investigator or study coordinator. Event, date of onset, severity, duration, and relationship to the procedure or device will be recorded.

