	
During Procedure (up to 2 ELS treatments):
 
Cystoscopy with local anaesthesia and light or moderate sedation or light general anaesthesia (investigator's discretion), placement of ureteral catheter, periodic fluoroscopic and/or diagnostic ultrasound imaging (at investigator's discretion), intraluminal ureteral placement of ELS Acoustic Enhancer material and administration of acoustic energy. Multiple repetitions of ELS Acoustic Enhancer placement-insonation cycle will be performed
 
Follow-up:
 
1, 2, 3, 7 days (telephone follow-up): Assess pain and pain medications, evaluate for AEs
 
14 (\pm 4) days (on site exam): KUB X-ray and ultrasound; physical exam; assess pain and pain medications; urine culture; evaluate for AEs; Assess for eligibility for 2nd ELS Treatment (i.e. treated stone/fragment is \geq 3 mm and subject remains eligible per I/E criteria)
 
30 (\pm 4) days after last ELS procedure: CT scan (non-contrast) to evaluate stone status; physical exam; assess pain and pain medications; evaluate for AEs; serum creatinine; Assess for eligibility for 2nd ELS Treatment
 
Treatment 2 (if necessary): Repeat ELS treatment if subject meets eligibility criteria (i.e. treated stone/fragment is \geq 3 mm and subject remains eligible per I/E criteria). If performed, repeat Day 1, 2, 3, 7, 14 & 30 Follow-Up visits
 
90 (\pm 21) days: physical exam; serum creatinine; evaluate for AEs and record medications; renal-bladder ultrasound for safety assessment

Primary Endpoint	Treatment success: Proportion of study participants who, after up to 2 ELS treatments, have a complete absence of stones or with any residual fragments measuring less than 3 mm in the largest dimension as assessed by follow-up imaging through 30 day follow-up after last ELS procedure
Secondary Endpoints	
 • Proportion of participants with Serious Device and/or Serious Procedure-Related AEs from initial ELS Treatment through 30 days following last ELS treatment • Proportion of participants with Serious Device and/or Serious Procedure-Related AEs from initial ELS Treatment through 90 days following last ELS treatment • All AEs & SAEs from initial ELS Treatment through 30 days following last ELS treatment • All AEs & SAEs from initial ELS Treatment through 90 days following last ELS treatment • Participant satisfaction at 30 day follow-up following last ELS treatment

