5.2 Secondary Endpoints

- Proportion of participants with Serious Device and/or Serious Procedure-Related AEs from initial ELS Treatment through 30 days following last ELS treatment.
- Proportion of participants with Serious Device and/or Serious Procedure-Related AEs from initial ELS Treatment through 90 days following last ELS treatment.
- All AEs & SAEs from initial ELS Treatment through 30 days following last ELS treatment
- All AEs & SAEs from initial ELS Treatment through 90 days following last ELS treatment
- Participant satisfaction at 30 day follow-up following last ELS treatment

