As with any procedures in which cystoscopes and other instruments are inserted into the urinary tract and materials placed using a cystoscope (small tube) into the urinary tract, in very rare cases, portions of the urinary tract could become inflamed or infected. There is also the risk of inadvertently pushing a urinary stone from the urinary tract into the kidney and of ureteral perforation from passage of the ureteral catheter.

Significant new findings that may affect the participant's safety or willingness to continue in the study will be communicated to the study doctors and study participants. An updated informed consent may be administered if appropriate.

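### Section 8.3 opens adverse-event reporting at Enhancer entry, after the index procedure has begun; this conflicts with the safety endpoints and other recording rules, so early procedural events may go uncaptured

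*Combined protocol and SAP*

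**What the plan says.** Section 8.3 (Assessment and Documentation of Adverse Events) contains the only explicit start of reporting in the protocol: "All adverse events will be reported from the moment a consented participant has ELS Acoustic Enhancer material enter the body". Reporting then continues until the participant leaves the study.

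The same section also carries two sentences without that limit: "Any adverse event (whether or not related to the investigational device) or device deficiency should be recorded on the appropriate eCRF", and "Adverse event information will be collected throughout the study".

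Section 5.2 sets the first safety endpoint as "Proportion of participants with Serious Device and/or Serious Procedure-Related AEs from initial ELS Treatment through 30 days following last ELS treatment". A second endpoint extends the window to 90 days, and two more count all AEs and SAEs over the same two windows. The protocol does not say at what moment the initial ELS treatment starts.

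The synopsis describes the procedure as beginning with "Cystoscopy with local anaesthesia and light or moderate sedation or light general anaesthesia", followed by ureteral catheter placement, imaging and then Enhancer placement. Section 3.1 says that Enhancer is injected by syringe through a catheter already positioned by cystoscopy. Among the risks in section 7.1 are reactions to anaesthesia, the general hazards of sedation and anaesthesia up to death, and the risk "of ureteral perforation from passage of the ureteral catheter".

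**The concern.** The index procedure is under way before the 8.3 window opens. An anaesthetic reaction, or a perforation while the catheter is being passed, can occur before any Enhancer has been given. If such an event ends the procedure, Enhancer never enters and the 8.3 trigger is never met for that participant.

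The endpoints in 5.2 are meant to capture serious events related to the procedure as well as to the device. If sites apply the 8.3 start, part of the procedure drops out of the numerator. Section 11.1 analyses all enrolled participants and defines enrolment at consent, so an aborted participant could stay in the denominator while the event is missing. The safety proportion would then be biased low. Sites that read the passages differently would also collect different data, and a monitor would have no clear basis for querying a missing early event.

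Showing safety is a stated purpose of the study. Section 2.2 intends the data for marketing applications and cites earlier experience of 0 device-related serious events in 13 participants. On numbers this small, one event matters.

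**Working it through.** **Step 1. Order of events at the index procedure.** The synopsis and section 3.1 together give: (a) sedation or anaesthesia and cystoscopy; (b) ureteral catheter placement; (c) Enhancer through that catheter, then acoustic energy, repeated. Reporting under the 8.3 start opens at (c). The risks quoted from 7.1 belong to (a) and (b).

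**Step 2. Recording rules side by side.**

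| Place | Start of recording | Covers (a) and (b) at the index procedure? |
|---|---|---|
| 8.3, reporting sentence | Enhancer enters the body | No |
| 8.3, general recording sentence | none stated | Can be read as yes |
| 8.3, collection sentence | throughout the study | Yes |
| 5.2, safety endpoints | initial ELS treatment, start undefined | Probably; 6.2.1 describes anaesthesia as part of treatment |
| 6.2.1, ELS Treatment | AEs recorded, no start stated | Can be read as yes |
| 8.4, SAE reporting | SAE form within 24 hours, no start stated | Yes, for serious events only |
| Table 2 | AE reporting ticked for the ELS Treatment visit | Can be read as yes |

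The one rule with an explicit starting moment disagrees with the others, and no passage says which governs.

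**Step 3. Extent of the gap.** Once Enhancer has entered at the index procedure, the 8.3 window runs to study exit. Anaesthesia, cystoscopy and catheter events at a second ELS treatment therefore fall inside it. The gap is limited to the part of the index procedure before Enhancer, plus index procedures abandoned in that interval.

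**Step 4. Size.** No figure in the plan depends on the reporting start, so there is none to reproduce, and no rate is given for pre-Enhancer events. The number treated is not stated either. I bracket it by 58, the number evaluable for the primary efficacy endpoint, and 75, the maximum enrolled (section 11.6 and synopsis).

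One missed serious event:
- 1/58 = 1.7 percentage points
- 1/75 = 1.3 percentage points

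Exact (Clopper-Pearson) 95% intervals. For zero events the upper limit is 1 − 0.025^(1/n).

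| Treated | One event, captured | Same event, not captured |
|---|---|---|
| 58 | 1.7% (0.04 to 9.2%) | 0% (0 to 6.2%) |
| 75 | 1.3% (0.03 to 7.2%) | 0% (0 to 4.8%) |

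Chance that at least one such event occurs, 1 − (1 − q)^n, for **assumed** per-participant rates q of a serious pre-Enhancer event:

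| q | n = 58 | n = 75 |
|---|---|---|
| 0.5% | 25% | 31% |
| 1% | 44% | 53% |
| 2% | 69% | 78% |

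This is the chance that an event occurs, not that it goes unrecorded. The latter depends on which passage a site follows.

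**Step 5. Effect on the tests.** Section 11.4 reports the secondary endpoints descriptively, and the study success criterion in the synopsis concerns treatment success only. Alpha, power and sample size are unaffected.

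**The case against.** The strongest reply is that the 8.3 sentence is poor wording overridden by everything around it. Section 8.4 requires an SAE form for any serious event, related or not, with no Enhancer condition. Section 6.2.1 and Table 2 call for AE recording at the treatment visit. Under section 9, monitors compare eCRFs with medical records. A serious anaesthetic or catheter event could well be captured.

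Much of this stands. A reader might infer that pre-Enhancer serious events are certainly lost, or that they escape SAE reporting altogether. The documents do not support that, because 8.4 and the other sentences of 8.3 can be read to require recording. A reader might also infer that the endpoint itself leaves out the early steps. It does not: 5.2 starts at the initial ELS treatment, and only the reporting sentence of 8.3 conflicts with it.

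The reply does not remove the problem. None of the other passages names a starting moment, so a site may reasonably treat the one that does as governing. Section 8.4 helps only with serious events; for non-serious ones, which enter the all-AE endpoints, the contradiction remains open.

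A further tempting inference is that section 8.2 deepens the bias by limiting device- or procedure-related events to the two highest grades of relationship (the definition reads "will be defined as adverse events graded" and then names probable and highly probable). I would not press this. The cut-off is prespecified, 5.2 also counts all AEs and SAEs whatever their cause, and 11.4 tabulates events by seriousness and relatedness and lists every one. Events graded possible remain visible, and a different threshold is a matter of preference.

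**Conclusion.** The point holds as an internal contradiction that puts capture at risk; it does not establish that events are excluded. It affects only the pre-Enhancer part of the index procedure and index procedures aborted before Enhancer. Where a site follows the explicit 8.3 start, the bias in the descriptive safety proportions is downward.

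The actual size cannot be calculated from the documents. The illustration of 1.3 to 1.7 percentage points per missed serious event assumes between 75 and 58 treated participants. The event rates of 0.5 to 2% in the working are my assumptions. The conclusion that the passages conflict depends on none of these numbers. Because safety data are at stake and the correction is cheap, it should be made.

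**What to change.** - In 8.3, start AE and SAE reporting at the start of the first ELS procedure, defined as the first sedative, anaesthetic or instrumentation, whichever is earliest, whether or not Enhancer is given.
- Use that same moment to define the start of the initial ELS treatment in 5.2, and align 6.2.1, 8.4 and Table 2 with it.
- State that participants whose procedure is aborted before Enhancer stay in the safety analysis, in both numerator and denominator.
- Leave the relatedness threshold in 8.2 unchanged.

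The cost is minor protocol wording and eCRF guidance. A few more events may be recorded, and the reported safety rate may be slightly less favourable. Sample size and the primary analysis do not change.

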7. RISKS AND BENEFITS

7.1 Potential Risks

The potential risks associated with the ELS procedure are expected to be similar or less than those of traditional SWL procedures used to treat urinary stones. Potential adverse events, which may be associated with the ELS and ELS Acoustic Enhancer material, and medications prescribed for use during these procedures include:

- Haematuria
- Pain or discomfort
- Skin redness where the treatment head is held against the body or from the belt that may be used to hold the treatment head in place
- Sensitivity/Tenderness over the treatment area
- Urinary blockage from stone fragmentation
- Bruising of tissue along the path of acoustic energy entering the body
- Urinary tract infection or inflammation
- Fever
- Mild cardiac arrhythmia could result from acoustic energy
- Bruising or damage to the kidneys, or tissue near the kidneys
- Allergic or anaphylactic reaction.
- Differential pressure risks include pressure from backflow of urine in the urinary tract system, and in rare cases rupture in the urinary tract

The procedure is also associated with potential anesthesia risks:

- Reaction to anesthesia
- Bleeding at anesthesia site
- As with any procedure performed with sedation or anaesthesia, there is risk associated that includes heart attack, stroke, and even death.

As with shock wave lithotripsy for urinary stones, the following adverse events may occur while being treated with ELS:

- Common (estimated as greater than 20% of patients)¹
 - There may be mild bleeding (including blood in the urine) or irritation from the ELS procedure. In rare cases, transfusion may be required to address bleeding.
 - There could be pain associated with the ELS sound wave energy effects and resulting stone fragments, with placement and movement of instruments in the urinary tract, or from other aspects of the procedure.
 - There could be skin redness around where the treatment head was held during the procedure, or irritation or bruising of the skin from the belt used to hold the treatment head in place during the procedure.

¹ Estimated occurrence rates are referenced from FDA, Center for Devices and Radiological Health: Guidance for the Content of Premarket Notifications (510(k)s) for Extracorporeal Shock Wave Lithotripters Indicated for the Fragmentation of Kidney and Ureteral Calculi (August 9, 2000)

- Occasional (estimated as 1-20% of patients)

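### The adverse event start point in Section 8.3 (Enhancer entry) conflicts with the Section 5.2 safety endpoints and the other recording rules, so first-session events before Enhancer placement can be missed

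*Combined protocol and SAP*

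**What the plan says.** Section 8.3 gives the protocol's one explicit start event for adverse event reporting: "All adverse events will be reported from the moment a consented participant has ELS Acoustic Enhancer material enter the body". The same sentence ends the window at study exit.

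The first serious-event endpoint in Section 5.2 has a different start: "Proportion of participants with Serious Device and/or Serious Procedure-Related AEs from initial ELS Treatment through 30 days following last ELS treatment". A second serious-event endpoint runs to 90 days, and two further endpoints cover all AEs and SAEs over the same two periods. All four start at initial ELS Treatment. No section says whether that means the start of the procedure or the entry of Enhancer.

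Other rules carry no Enhancer condition:
- Section 8.3, the sentence just before the start rule: "Any adverse event (whether or not related to the investigational device) or device deficiency should be recorded on the appropriate eCRF".
- Section 8.3, later: "Adverse event information will be collected throughout the study".
- Section 6.2.1, which describes the treatment visit including sedation and anaesthesia, asks for AEs to be recorded.
- Table 2 ticks AE reporting in the ELS Treatment column.
- Section 8.4 asks for the SAE pages within 24 hours for any serious event, related to the device or not.

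**The concern.** The start event in 8.3 comes partway through the procedure. The steps before it carry harms that the protocol itself attributes to the procedure, and the most serious of those harms could end the session before any Enhancer is placed. If sites take 8.3 as the operative rule, the events missed are ones that the procedure-related endpoints exist to count, and the error runs in one direction only.

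Demonstrating safety is part of the stated purpose in the synopsis, and Section 2.2 says the data will support premarket applications. Section 11.4 reports the safety endpoints descriptively, so the result is only as good as the capture of events. With up to eight sites, different readings of the same section could also make capture uneven. An event not recorded at the time may not be recoverable at analysis.

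**Working it through.** This is mainly a consistency check. The plan states no figure to reproduce.

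**Step 1: order of the procedure.** The synopsis begins the procedure with "Cystoscopy with local anaesthesia and light or moderate sedation or light general anaesthesia", then lists ureteral catheter placement, and only then Enhancer placement and acoustic energy. Section 3.1 confirms the order: the Enhancer is given by syringe through a catheter already positioned at cystoscopy. At a first session, sedation or anaesthesia, cystoscopy and catheter placement all precede the 8.3 start event.

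**Step 2: are harms from those steps procedure-related?** Section 7.1 says so: "The procedure is also associated with potential anesthesia risks", and the list that follows goes up to heart attack, stroke and death. It also names the risk "of ureteral perforation from passage of the ureteral catheter". Section 8.2 grades relationship to the procedure separately from relationship to the device (Table 4), so such events could qualify for the Section 5.2 endpoints.

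**Step 3: who falls in the gap on a literal reading of 8.3?**
- First session, event before Enhancer entry, Enhancer then placed: the event precedes the window.
- First session aborted before Enhancer, and Enhancer never given later: the participant never enters the window. Section 7.1 foresees rescheduling after equipment malfunction, but no rule covers AEs from an aborted session.
- Second session after Enhancer was placed at the first: the window is already open and runs to study exit, so events before Enhancer at the second session are inside it, even if that session is aborted.

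The gap is therefore confined to the period before the first Enhancer entry.

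**Step 4: size, by illustration.** The documents give no rate for events before Enhancer placement. Assume one serious event of this kind, no other serious related event, and that the event is not reported. Section 11.6 gives 58 evaluable participants and 75 enrolled. Neither is a count of treated participants, so they serve only as a plausible range for the denominator.

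Exact two-sided 95% upper limits (Clopper-Pearson):
- With 0 events the limit is 1 − 0.025^(1/n). For n = 58 this is 6.2%; for n = 75, 4.8%.
- With 1 event the limit solves (1 − p)^n + n·p·(1 − p)^(n−1) = 0.025. For n = 58 this is 9.2%; for n = 75, 7.2%.

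| Denominator | Event counted | Event omitted | Change in rate | Change in upper limit |
|---|---|---|---|---|
| 58 | 1/58 = 1.7%, upper 9.2% | 0/58, upper 6.2% | 1.7 points | about 3.1 points (9.24 − 6.16) |
| 75 | 1/75 = 1.3%, upper 7.2% | 0/75, upper 4.8% | 1.3 points | about 2.4 points (7.21 − 4.80) |

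If the participant with the aborted session also left the denominator, the reported result would be 0/57, with upper limit 1 − 0.025^(1/57) = 6.3%. That is almost the same as 0/58, so the missing event matters far more than the missing participant.

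**The case against.** The strongest reply is that 8.3 does not say reporting is confined to the period after Enhancer entry, and that the rest of the protocol points the other way. The sentence before it covers any AE, 6.2.1 and Table 2 cover the treatment visit, and 8.4 requires every SAE within 24 hours. The main endpoints at issue count serious events, so 8.4 bears on them directly. Section 5.2 also has its own window, and nothing says that 8.3 overrides it. The endpoints are secondary and descriptive, with no safety performance goal, and an independent medical advisor reviews SAEs.

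Much of this stands. It shows a conflict between passages, not a clear exclusion, and it makes complete loss of serious events less likely. It does not remove the problem. None of the other rules names a start event, so a site can reasonably read them as subject to the one that does. Non-serious events, which two of the four endpoints count, do not have the 8.4 route.

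Three stronger readings are tempting, and the documents do not support them:
- A reader might infer that every session aborted before Enhancer placement is lost. Step 3 shows that this fails for a second session after Enhancer was placed at the first.
- A reader might infer that the serious procedure-related rate is certain to be biased low. That requires such an event to occur and the site to follow one sentence of 8.3 over 6.2.1, Table 2 and 8.4.
- Because Table 2 has no AE tick at screening, a reader might add events from medication changes before treatment. These precede ELS Treatment, lie outside the 5.2 window and cannot bias those endpoints.

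**Conclusion.** The concern holds as an internal conflict that should be fixed. The start event in 8.3 is later than the start of the procedure and does not match the 5.2 endpoints or the unconditional recording rules. Followed literally, it can omit first-session anaesthesia, cystoscopy and catheter events, and it leaves out a participant whose first session is aborted and who never receives Enhancer.

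Any loss would lower the reported rate. Per omitted serious event, this is about 1.3 to 1.7 percentage points on the rate and 2.4 to 3.1 points on the exact upper limit. That size rests on an assumed single event, on its going unreported despite 8.4, and on a denominator between 58 and 75. The documents do not show how likely such an event is. The text of the conflict is certain; its effect on the result is only possible.

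**What to change.** Reconcile the passages around one start point:
- In 8.3, begin AE reporting no later than the start of the first sedation, anaesthesia or cystoscopy undertaken for ELS treatment.
- In 5.2, define initial ELS Treatment as that same moment.
- In 5.2 or 11.4, state that participants with an attempted but aborted first session stay in the safety count and the safety denominator, whether or not Enhancer was placed.
- Check that 6.2.1, Table 2, 8.4 and the eCRF instructions use the same start.

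The cost is a wording change in the protocol and eCRF guidance, a few more AEs to record, and possibly a less favourable safety rate. No procedure, visit or sample size changes.
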